- **H2:** A higher proportion of the new NF swabs with 5 cm insertion will be adequate for cytopathology interpretation compared to the NF swab for 3 cm insertion.
- **H3:** The new NF swab will have molecular adequacy that is commensurate with the original NF swab used in the PAC Self-Swab Study.
- **H4:** The new NF swab will have acceptability/pain performance commensurate with the originally proposed NF swab and the 5 cm insertion depth will have similar acceptability/pain performance as the 3 cm insertion depth.

Our expected outcomes are cytological and molecular preliminary performance characteristics of the new NF swab in addition to user acceptability. These outcomes will help ensure the use of a viable swab in SOLO that is relevant in future anal cancer screening programs.

B Pilot Study Objective and Endpoints

B.1 Pilot Study Objective

To ensure the use of a swab in SOLO that is comparable to the originally proposed swab for SOLO, determine the preliminary performance characteristics of the new NF swab.

B.2 Pilot Study Endpoints

1. A comparison of the proportions of individuals who collect squamocolumnar cells when using a NF swab with a 5 cm vs. a 3 cm insertion depth.
2. A comparison of the proportions of individuals who collect cytologically adequate specimens when using a NF swab with a 5 cm vs. a 3 cm insertion depth.
3. A comparison of the proportions of individuals who collect adequate specimens for molecular genotyping when using the new NF swab vs. the original swab used in the PAC Self-Swab Study.
4. A comparison of the acceptability and pain performance of the new NF swab vs. the original swab and the 5 cm and 3 cm insertion depth.

C Pilot Study Eligibility

The pilot study team will evaluate eligibility according to the following criteria. Individuals must meet all inclusion and none of the exclusion criteria to be registered on to the pilot study. Any questions or concerns regarding eligibility should be directed to the PI, [name] ([contact]).

C.1 Inclusion Criteria

A potential pilot study subject who meets all of the following inclusion criteria is eligible to participate in the pilot study. Note that these criteria apply regardless of HPV vaccination status or disability status.

1. Aged \geq 35 years.
2. Must be either:
 - a) A cisgender or transgender sexual minority man, or
 - b) A transgender woman who has sex with men.
3. Resides in the Milwaukee metropolitan area.
4. Speak and understand English.

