Potential participants will be screened using an online computer-assisted self-interview (CASI). Those who are eligible will be asked to leave contact information. Study staff will contact eligible individuals, provide an overview of the pilot study, and invite the individual to a schedule a consenting session which will be followed by the cytology screening at the Curative Building on the MCW campus. Those who are not eligible will be thanked for their interest and provided links to vetted anal cancer education websites. Minimal Protected Health Information (PHI) will be collected in the eligibility survey.

At the consenting session staff will first ask the eligible individual to confirm their email address, name, and birthdate. The session will occur in a closed office and include information about 1) high rates of anal cancer in SGM, 2) anal cancer screening and the role of swabbing, 3) pilot study activities, and 4) the potential harms and benefits of participation. The staff member obtaining consent will emphasize that participation is voluntary and that participants can choose to join and,

if desired, leave the pilot study at any point without any repercussions. The ICF will also notify individuals that we will collect their street address to support payment using the MCW visa card.

Prior to obtaining their signature, the staff member will ask the individual if they have any questions and, if not, to briefly review their understanding of their participation by asking simple questions about the pilot study to be sure the information was clearly understood.

Individuals agreeing to provide consent will sign an ICF hard copy. It will be photocopied with the copy given to the participant.

F Pilot Study Design and Intervention

F.1 Study Design

This pilot feasibility study will use a randomized controlled trial design.

Figure 1 illustrates the pilot study design.

F.2 Randomization

Consented individuals will be randomized to either the intervention (5 cm insertion depth) or the control (3 cm insertion depth) arm using a number generator in REDCap. If the number is .0000 to .4999, the individual will be assigned to the intervention condition. If the number is .5000 to .9999, the individual will be assigned to the control condition.

The participant is considered enrolled in the pilot study when they sign a consent form and are randomized to either the intervention or control arm.

F.3 Cytology Sampling

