1. A comparison of the proportions of individuals who collect squamocolumnar cells when using a NF swab with a 5 cm vs. a 3 cm insertion depth.
2. A comparison of the proportions of individuals who collect cytologically adequate specimens when using a NF swab with a 5 cm vs. a 3 cm insertion depth.
3. A comparison of the proportions of individuals who collect adequate specimens for molecular genotyping when using the new NF swab vs. the original swab used in the PAC Self-Swab Study.
4. A comparison of the acceptability and pain performance of the new NF swab vs. the original swab.

H.2 Power for Endpoints

This pilot feasibility study does not have the power to make conclusive statements about the study endpoints.

H.3 Analysis Plan

H.3.1 Preliminary analyses

We will assess the success of randomization. For surveys, we will calculate item response rates for each arm of the study and for subgroups based on HIV status, race/ethnicity, and education.⁴³

After evaluating missing survey data, we will use multiple imputation⁴⁴ to maintain the maximum sample size if data are missing at random. Sensitivity analyses will compare results if data are not missing at random.⁴⁵

In each study arm, we will analyze frequencies of survey items, demographics, other domains, adverse events, and serious adverse events.

H.3.2 Primary Endpoint 1

The presence of cells from the squamocolumnar junction will be assessed in each specimen (Yes/No). Proportions of specimens with squamocolumnar cells will be compared for the 5 cm and 3 cm swabs.

H.3.3 Primary Endpoint 2

Cytologic adequacy is defined as the presence of ~2000-3000 nucleated squamous cells. Proportions of adequate specimens will be compared for the 5 cm and 3 cm swabs.

H.3.4 Primary Endpoint 3

The PAC Self-Swab Study molecular adequacy estimates, given study size, were quite precise with narrow confidence limits. The estimates derived from this pilot study will have wider confidence limits. The original and new swabs will be considered to have commensurate molecular adequacy if the exact confidence limits of the original PAC Self-Swab Study swab are covered by the exact confidence limits of the piloted swab.

H.3.5 Primary Endpoint 4

Each participant will receive a short cytology CASI immediately after the cytology screening to rate their acceptability of the cytology screening on a Likert scale and pain on a visual scale.³⁷ Proportions of individuals' ratings for adequacy and pain will be compared for

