- 1) the 5 cm and 3 cm swabs, and
- 2) the new NF swab vs the original swab.

The Exact 95% confidence limits surrounding proportions for acceptability and pain will be compared for overlap for 5 cm vs 3 cm insertion depths.

The comparison of acceptability/pain between the new NF swab and the original swab will be analyzed as in H.3.4.

I ADVERSE EVENTS AND OTHER REPORTABLE INCIDENTS

This study is low risk to participants due to its design and the nature of the intervention being tested (i.e., cancer screening and behavioral interventions). No investigational drugs or devices are involved.

Even though this study does not test a therapeutic intervention, this study will follow the Cancer Therapy Evaluation Program (CTEP) guidelines for reporting of adverse events. All expedited adverse event reports are required to be submitted to the MCW Institutional Review Board (IRB).

I.1 Definitions

I.1.1 Adverse Event (AE)

Any untoward medical occurrence in an individual or clinical investigation subject administered an interventional product and which does not necessarily have to have a causal relationship with this intervention.

This study will utilize the NCI Common Terminology Criteria for Adverse Events (CTCAE) version 5.0, located on the CTEP web site:

https://ctep.cancer.gov/protocolDevelopment/electronic_applications/ctc.htm

AEs may be spontaneously reported by the subject and/or in response to an open question from study personnel or revealed by observation, physical examination or other diagnostic procedures.

I.1.2 Serious Adverse Event (SAE)

Serious Adverse Event (SAE) means any untoward medical occurrence that results in any of the following outcomes:

- **Death.** Results in death.
- **Life-threatening.** Is life-threatening (refers to an AE in which the participant was at risk of death at the time of the event. It does not refer to an event which hypothetically might have caused death if it were more severe).
- **Hospitalization.** Requires inpatient hospitalization ≥ 24 hours or prolongation of an existing hospitalization.
- **Disability/incapacity.** Results in persistent or significant disability or incapacity. (Disability is defined as a substantial disruption of a person's ability to conduct normal life functions).
- **Pregnancy**

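### Comparing 5 cm with 3 cm on acceptability and pain by overlap of separate intervals misses large differences and cannot show similarity; report the difference with its own CI

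*Combined protocol and SAP*

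**What the plan says.** Hypothesis H4 in section A predicts that "the 5 cm insertion depth will have similar acceptability/pain performance as the 3 cm insertion depth". The same section raises the possibility that deeper insertion makes the swab less acceptable without improving the specimen.

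Section H.3.5 says that proportions of ratings will be compared between the two depths. The only method it names is that the exact 95% "confidence limits surrounding proportions for acceptability and pain will be compared for overlap for 5 cm vs 3 cm insertion depths". It gives no between-arm difference, no CI for one, no test, no definition of similar, and no statement of what overlap or non-overlap would mean. The verdict rule in H.3.4, under which the swabs "will be considered to have commensurate molecular adequacy if the exact confidence limits" meet a coverage condition, is carried over only to the comparison of new with original swab.

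Three other places bear on the point:

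- H.3.1: "In each study arm, we will analyze frequencies of survey items", so per-arm frequencies are planned.
- H.2: "This pilot feasibility study does not have the power to make conclusive statements about the study endpoints".
- Endpoint 4: the summary and B.2 include the depth comparison ("vs. the original swab and the 5 cm and 3 cm insertion depth"), while H.1 lists only "A comparison of the acceptability and pain performance of the new NF swab vs. the original swab".

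**The concern.** Two separate 95% intervals can overlap while the 95% CI of the difference excludes zero. As a way to find a difference, the overlap check is therefore much stricter than 5%. As a way to support H4 it errs in the other direction: small arms give wide intervals, and wide intervals nearly always overlap.

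At stake is the plan's own question of whether 5 cm costs acceptability. A report that the intervals overlap, placed beside a hypothesis of similar performance, invites the reader to conclude that depth makes no difference. The data in hand may show a gap of 30 points or more.

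**Working it through.** The plan states no error rate or power for this comparison, so there is no figure to reproduce.

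**Inputs**

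- Total of 60 participants (section D).
- Allocation by an unrestricted random number (F.2: "If the number is .0000 to .4999, the individual will be assigned to the intervention condition"). The plan fixes no arm size. I take 30 per arm as the main case; the central 95% range for one arm is 22 to 38.
- True proportions: none are given, so 90 vs 60, 80 vs 50 and 90 vs 70 (percent) are assumptions chosen to show a range.

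**Formulas**

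- Exact (Clopper-Pearson) limits for x of n: lower is the 2.5% point of Beta(x, n−x+1); upper is the 97.5% point of Beta(x+1, n−x). Overlap means that neither lower limit exceeds the other arm's upper limit.
- Newcombe limits, with Wilson limits (l, u) in each arm and d = p1 − p2: from d − √[(p1−l1)² + (u2−p2)²] to d + √[(u1−p1)² + (p2−l2)²].

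**One table in full: 27/30 vs 17/30**

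- Exact limits are 0.735 to 0.979 and 0.374 to 0.745. Since 0.745 exceeds 0.735, they overlap.
- Wilson limits are 0.744 to 0.965 and 0.392 to 0.726, and d = 0.900 − 0.567 = 0.333.
- Lower: 0.333 − √(0.156² + 0.160²) = 0.333 − 0.223 = 0.110.
- Upper: 0.333 + √(0.065² + 0.175²) = 0.333 + 0.187 = 0.520.
- Fisher p = 0.007. With 16/30 in the lower arm the overlap ends.

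**Largest observed gap that still overlaps, for three upper-arm counts**

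| Counts | Difference (points) | Newcombe 95% CI | Fisher p |
|---|---|---|---|
| 30/30 vs 23/30 | 23 | 7 to 41 | 0.011 |
| 27/30 vs 17/30 | 33 | 11 to 52 | 0.007 |
| 25/30 vs 14/30 | 37 | 13 to 56 | 0.006 |

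**All 31 × 31 = 961 tables at 30 per arm**

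- The intervals fail to overlap in 424. In every one of these the Newcombe CI also excludes zero.
- The Newcombe CI excludes zero in 592, so there are 592 − 424 = 168 tables where the intervals overlap but the difference CI excludes zero.
- The largest Fisher p among the non-overlapping tables is 0.0056.

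**Probabilities at 30 per arm (sums of binomial products)**

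| True rates (%) | Intervals overlap | Newcombe excludes 0 | Both | Fisher p ≤ 0.05 |
|---|---|---|---|---|
| 90 vs 60 | 61% | 79% | 40% | 71% |
| 80 vs 50 | 72% | 69% | 41% | 60% |
| 90 vs 70 | 86% | 49% | 35% | 37% |

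With equal true rates, the maximum over 1% to 99% is 0.3% for non-overlap, 5.2% for Newcombe and 2.7% for Fisher.

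**Unequal arms.** Averaging over simple randomisation of 60 gives overlap / Newcombe excludes zero of 63% / 79%, 72% / 69% and 88% / 48% in the same three cases. Over splits from 22/38 to 38/22, the largest gap that still overlaps runs from 21 to 39 points, and none of the 6,900 non-overlapping tables has a Newcombe CI that includes zero.

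**What the difference CI can show.** With identical results in both arms it spans about ±17 points (27/30 each), ±20 (24/30 each) and ±24 (15/30 each).

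**The case against.** The strongest reply is that the plan draws no conclusion from overlap. H.3.5 attaches no verdict to it, H.2 disclaims conclusive statements, and H.3.1 already plans per-arm frequencies, from which a reader could work out any difference CI. All of that is true, and it is why the point is minor. It does not make overlap a sound summary: the masking occurs in the same 60 participants and comes from the choice of method.

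A second reply is that the replacement cannot establish similarity either, and that H4 has no margin. This stands. The difference CI will be wide, and the gain is that the width becomes visible.

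Third, part of the insensitivity is sample size: at 90 vs 70 the difference CI also fails to exclude zero in about half of trials. The comparison of detection rates also sets a rule with a 0.3% null rate beside one with about 5%, and with several items each interval carries its own rate. Both are fair, and they are reasons to keep the comparison descriptive.

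Finally, H.3.5 gives no cut-points for turning Likert and visual-scale ratings into proportions, and H.3.1 plans multiple imputation without saying how imputed proportions are handled. Both gaps affect the overlap check as much as its replacement.

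**Conclusion.** The concern holds, at minor severity. Overlap is the only method stated for this comparison. It is a valid but very conservative signal of a difference (null rate at most 0.3% at 30 per arm), and it gives no support to similarity. Observed gaps of 23 to 37 points, with difference CIs clear of zero, still overlap in the examples shown. Using the difference CI loses nothing that non-overlap would find.

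The table results assume 30 per arm but persist over the plausible splits. The detection rates also depend on assumed true proportions. The mismatch between H.1 and the summary and B.2 over endpoint 4 is a secondary, editorial matter.

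**What to change.** Replace the overlap sentence in H.3.5 with:

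> For 5 cm vs 3 cm, the difference in each acceptability and pain proportion (5 cm minus 3 cm) will be reported with a Newcombe 95% CI, using response categories fixed before data are seen. The comparison is descriptive, and overlap of the separate intervals, or a difference CI that includes zero, will not be read as showing similarity.

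Make endpoint 4 in H.1 agree with the summary and B.2 on whether the depth comparison belongs to it. If survey data are imputed under H.3.1, say how the difference and its CI are pooled.

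The cost is a few sentences of wording and a few lines of code on data already planned, with no extra participants. There are two downsides. The Newcombe interval is approximate, with a null rate of up to 5.2% at 30 per arm and 5.6% over splits from 22/38 to 38/22. And the pilot will rarely be able to support a claim of similarity.

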The cytology sampling will occur immediately after randomization. In preparation, staff will have created two cytology collection kits (labeled as Kit A or Kit B) each containing swabbing instructions, a swab, ThinPrep vial, and gloves. Kit A and Kit B will have identical contents except that Kit A will have a swab with a colored mark 5 cm from the swab tip and Kit B will have a swab with a colored mark 3 cm from the swab tip.

Clinical staff will review the sampling instructions with the individual and then show them to a bathroom in Curative with a locking door where they will do the self-sampling with sampling instructions available. Individuals will be instructed to take the cap off the vial, put on gloves, remove the swab from the packaging, hold the swab at the marker on the shaft of the swab (which corresponds to either 3 cm or 5 cm), get in a comfortable position, insert the swab gently all the way to the mark, begin to twirl the swab clockwise and counterclockwise, and apply pressure to the anal canal walls, while removing the swab as they count slowly to 10.

[figure not shown]

Figure 1. Pilot study schema.

After swabbing, the participant will put the swab in 20 mL of PreservCyt® solution, agitate and twirl it in the solution for 10 seconds, and then remove the swab while pressing against the sides of the vial. The swab will be discarded, the vial cap replaced, and the vial inserted back into the Kit and returned to the staff member. Participants will be instructed to wash their hands.

Participants will complete a short CASI in the consenting office in private on their phone (or hard copy if they prefer) immediately after their self-sampling to assess the swabbing experience, including discomfort and pain, using validated questions. Clinic staff will assist individuals with technology limitations. Participants will then receive \$40.

For those who do not show up for their consenting and cytology appointment, a member of the study team will contact them twice to reschedule within 2 months of their original appointment date.

F.4 Kit Processing, Cytopathology, and Genotyping

Staff will walk the cytology kit to the MCW Tissue Bank who will process the PreservCyt liquid by removing a 0.5 mL aliquot for HPV genotyping. The remaining specimen will be kept in the original vial for cytopathology.

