The investigator may withdraw a participant whenever continued participation is no longer in their best interests. Reasons for withdrawing a participant include, but are not limited to, a participant's noncompliance, or simply significant uncertainty on the part of the investigator that continued participation is prudent.

F.5.3 Replacement Policy and Data Usage

[figure not shown]
Individuals who sign the informed consent form and are randomized, but subsequently withdraw, will be replaced. Data collected from individuals that withdraw or discontinue from the study will be used.

F.6 End of Pilot Study Definition

An individual is considered to have completed the study if they have completed the post-cytology survey. Those who participated in the pilot study will not be eligible or involved in the parent SOLO study.

G Pilot Study Team, Assessments, and Procedures

G.1 Pilot Study Team Structure

G.2 Pilot Study Schedule of Events

Procedures and Events	Recruitment	Consent & Cytology Appointment	End of Pilot Study
Eligibility Screening	X		
Informed Consent		X	
Randomization and Enrollment ¹		X	
INTERVENTION			
Self-sampling with a 5 cm nylon-flocked swab		X	
CONTROL			
Self-sampling with a 3 cm nylon-flocked swab		X	
RESEARCH PROCEDURES			
Adverse Events Collection ²	(SAEs only)	AEs collected from the start of the intervention to 30 days after the end of the intervention	
Cytology Appointment Computer-Assisted Self-Interview (CASI) ³			X

¹ After an individual has signed the informed consent form and been randomized to one of the study arms, they are considered enrolled in the study.

² Refer to Section 7.2 for adverse event (AE) collection and reporting requirements.

³ The cytology CASI will be given to participants immediately after they complete cytology collection.

G.3 Pilot Study Procedures to be Conducted by Site

Activity	Milwaukee		Tampa
	Medical College of Wisconsin	Wisconsin Diagnostic Labs	Moffitt Cancer Center
Funding	Primary Award	Service contract	Service contract
Recruitment	X	-	-
Consenting	X	-	-
Randomization	X	-	-
Participant interaction	X	-	-
Obtaining PHI	X	-	-
Surveying	X	-	-
Access to PHI	X	X	-
Supplying cytology kits	X	-	-
Cytology reading	-	X	-
HPV genotyping	-	-	X

Activity	Milwaukee		Tampa
	Medical College of Wisconsin	Wisconsin Diagnostic Labs	Moffitt Cancer Center
Key personnel	X	-	-

H Statistical and Epidemiological Considerations

H.1 Pilot Study Primary Endpoints

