The study investigator will be responsible for determining whether an AE is expected or unexpected as indicated in the protocol. An AE will be considered unexpected if the nature, severity, or frequency of the event is not consistent with the risk information previously described for the study intervention.

I.3 Collection and Reporting Requirements for Adverse and Serious Adverse Events

AEs that are Grade 3 or higher and are related (possibly, probably, or definitely) to the intervention will be collected from the time the subject starts the intervention through conclusion of the intervention, which comprises the cytology self-sampling and CASI. AEs will be tracked and followed until resolution, the subject withdraws consent or is lost to follow-up (including individuals who discontinue early). SAEs that occur after the subject has signed the consent form through 30 days after the conclusion of the intervention will be collected. Adverse events collected per the protocol should be followed with appropriate medical management.

AEs will be collected as reported. In the case of an adverse event, participants will be instructed to contact study staff and/or investigators as soon as possible, ideally within 24 hours. All Grade 3 and higher adverse events will be discussed with the PI and appropriate study staff. The PI will oversee that all AEs, SAEs, and UPIRSOs, are reported appropriately. Information about adverse events experienced by study individuals will be monitored by the following means:

- Report given by study participants to study staff, either in person or by telephone.
- Report given to study staff by study participants' family or friends, either in person or by telephone.
- Report by the participant's physician or other health care provider involved in the subject's care.
- Report from a hospital or other healthcare facility where the study participant is being treated for the serious adverse event.
- Other persons who may have knowledge of such a serious adverse event.

The PI will consult with other investigator(s) to assign event attribution category (unrelated, unlikely, possible, probable, or definite).

I.4 Institutional

Adverse and serious adverse events are not expected. If such events occur, AEs and SAEs will be reported per MCW Institutional Review Board (IRB) guidelines and the MCWCC Data and Safety Monitoring Plan (DSMP).

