The study monitor or other authorized representatives of the principal investigator may inspect all documents and records required to be maintained by the investigator.

K.5 Risk-Benefit Assessment

K.5.1 Potential Risks

HIV and anal cancer screening information is sensitive. All staff will have adequate training to appropriately handle participant data. The packaging of any needed mailings will comply with confidentiality standards. CASI data collection will use a web platform by REDCap with data stored on a secure web-based server at the Medical College of Wisconsin.

Potential risks to participants can be divided into three areas: 1) data collection using CASI, 2) concerns about disclosure of confidential, sensitive information, and 3) collection of anal canal cells and test results. These risks are described below.

1. CASI. This pilot study will ask sensitive questions of participants that may make some participants uncomfortable.
2. Potential disclosure of confidential, sensitive information. Some people may fear that unauthorized persons who may discriminate might obtain personal medical information or otherwise cause a change in the participant's social status or access to benefits to which participants would otherwise be entitled.
3. Collection of anal canal cells and test results. Some persons may feel embarrassed about inserting a swab into the anal canal. The swab can be uncomfortable, and occasionally there can be minor bleeding. Individuals will be notified of cytology results.
- 4.

There are no alternative screening procedures that are FDA-approved for anal cancer; however, cytology is now recommended by national and international bodies.

K.5.2 Potential Benefits

There is no benefit of this research to participants. However, they will learn about anal cancer and receive anal cytology results. Thus, the risk of discomfort during study procedures (either physical discomfort during clinical procedures or psychological discomfort due to sensitive survey

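### Section I.3 excludes minor bleeding, a named swab risk, from AE collection; no survey item on bleeding is named, and other sections state no grade limit

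*Combined protocol and SAP*

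**What the plan says.** - **Collection rule (I.3).** "AEs that are Grade 3 or higher and are related (possibly, probably, or definitely) to the intervention will be collected", from the start of the intervention "through conclusion of the intervention, which comprises the cytology self-sampling and CASI". Serious events have their own rule with no grade limit: "SAEs that occur after the subject has signed the consent form through 30 days after the conclusion of the intervention will be collected".
- **Reporting table (Table 1).** The non-serious columns cover Grades 3 and 4 only.
- **Named risk (K.5.1).** "The swab can be uncomfortable, and occasionally there can be minor bleeding".
- **Survey (F.3, H.3.5, K.6.3).** The CASI follows self-sampling immediately and is there "to assess the swabbing experience, including discomfort and pain, using validated questions"; H.3.5 adds acceptability. The items are not listed. K.6.3 says that most are taken from the earlier PAC Self-Swab Study surveys.
- **Analysis (H.3.1).** "In each study arm, we will analyze frequencies of survey items, demographics, other domains, adverse events, and serious adverse events".
- **Schedule (G.2).** "AEs collected from the start of the intervention to 30 days after the end of the intervention", with no grade or relatedness condition. Its footnote reads "Refer to Section 7.2 for adverse event (AE) collection and reporting requirements", but the protocol's sections are lettered A to L.
- **Other statements.** A later sentence in I.3 has AEs taken down as they are reported, and Section L has adverse events presented at weekly team meetings. Neither gives a grade limit.

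**The concern.** K.5.1 names two physical effects of swabbing. Discomfort has a planned measure in the CASI. Bleeding has none that any section names, and the operative sentence of I.3 excludes it if it is minor and non-serious. The participant swabs alone behind a locked door and discards the swab (F.3), and no section has staff look for or record blood. An unprompted report is therefore the main route by which a bleed would become known, and under I.3 it would still not qualify for collection.

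Insertion depth is the randomised factor, and K.5.2 says that the pilot informs the choice between 3 cm and 5 cm for SOLO. A reader of the H.3.1 output who sees no bleeds in either arm could take this as information about depth, when it would only reflect the collection rule.

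**Working it through.** The plan states no AE rate, and no power or sample-size figure on this point, so there is no figure to reproduce. The check sets the passages side by side and then adds an illustration.

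**Step 1: does a minor bleed meet the I.3 rule?** Two conditions apply, relatedness and Grade 3 or higher. A bleed caused by the swab meets the first. It fails the second if minor means below Grade 3. That is an inference: I.1.1 adopts CTCAE version 5.0 but does not reproduce the grades. Table 1 agrees with the threshold, so the I.3 sentence is not a stray phrase.

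**Step 2: do other sections bring it back in?**

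| Place | Grade limit for non-serious AEs | Window |
|---|---|---|
| I.3, operative sentence | Grade 3 or higher, related | Start of intervention to end of self-sampling and CASI |
| I.3, later sentence | None stated | None stated |
| G.2 | None stated | Start of intervention to 30 days after its end |
| Table 1 (reporting) | Grades 3 and 4 only | Not applicable |
| Section L (team review) | None stated | Weekly meetings |

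The places differ on threshold, and I.3 and G.2 also differ on window. The G.2 footnote does not settle it, because it points to a section number that does not exist in this protocol.

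**Step 3: is bleeding solicited elsewhere?** No section says so. The survey items are not listed, so an existing item cannot be ruled out.

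**Step 4: size, by illustration.** Inputs from the documents: 60 participants (Section D) and simple randomisation at probability 0.5 (F.2), so 60 × 0.5 = 30 expected per arm. The bleeding rate p is assumed, because K.5.1 says only that bleeding is occasional. Expected bleeds = 60p; chance of at least one = 1 − (1 − p)^60.

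| Assumed p | Expected among 60 | Expected per arm of 30 | Chance of at least one among 60 |
|---|---|---|---|
| 1% | 0.6 | 0.3 | 1 − 0.99^60 = 45% |
| 2% | 1.2 | 0.6 | 1 − 0.98^60 = 70% |
| 5% | 3.0 | 1.5 | 1 − 0.95^60 = 95% |
| 10% | 6.0 | 3.0 | 1 − 0.90^60 = 99.8% |

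Under the operative sentence of I.3, the number collected as AEs is 0 in every row.

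**Step 5: how an uncollected zero would look.** For 0 of 30, the exact two-sided 95% upper limit is 1 − 0.025^(1/30) = 11.6%. Attached to events that were never collected, that limit would carry no information.

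**Step 6: what full capture could show.** Normal approximation, two-sided 5%, n = 30 per arm, p̄ the mean of the two rates:

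power = Φ{[|p2 − p1| − 1.96 √(2p̄(1 − p̄)/n)] / √[(p1(1 − p1) + p2(1 − p2))/n]}

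- 5% versus 10%: (0.05 − 1.96 × 0.0680)/0.0677 = −1.23, power about 11%.
- 5% versus 20%: (0.15 − 1.96 × 0.0854)/0.0832 = −0.21, power about 42%.

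The approximation is rough at such small counts. It is enough to show that a by-depth contrast would remain descriptive.

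**The case against.** The threshold looks deliberate and proportionate. The study is classed as low risk, minor bleeding is a disclosed risk, and Table 1 uses the same grades. The drawback of depth that Section A itself raises is acceptability, which Endpoint 4 measures together with pain. No endpoint or decision rule uses AEs to choose a depth, H.2 disclaims conclusive statements, and every bleeding rate above is assumed. All of this stands. It makes the point modest but does not remove it: a physical effect that the protocol names still has no stated route into the by-arm tables.

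Three stronger readings are tempting, and the documents do not support them.

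- *Minor bleeds would never be recorded.* G.2, the later sentence in I.3 and Section L set no grade limit, and the survey items are unseen. If the CASI already asks about bleeding, the survey-item frequencies in H.3.1 would report it by arm.
- *The AE table would be empty.* Related AEs of Grade 3 or higher, and SAEs, would still appear. Only lower-grade events such as minor bleeds are at issue.
- *A planned safety comparison between depths is defeated.* H.3.1 plans frequencies in each arm and states no AE contrast.

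The unfiltered passages may also be read as subordinate to the I.3 threshold: Section L describes team review, not what enters the dataset. Because either reading is possible, the passages need to be reconciled.

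**Conclusion.** The point holds as a gap in the stated rule together with an inconsistency between sections. I.3, supported by Table 1, leaves minor bleeding out; no section names a solicited bleeding item; and G.2, the later sentence in I.3 and Section L do not carry the same limit. If I.3 governs, H.3.1 will show no minor bleeds in either arm at any true rate, against 0.3 to 3.0 expected per arm at assumed rates of 1% to 10%.

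This rests on three assumptions: minor bleeding is below Grade 3 and non-serious, the unlisted CASI items do not already cover it, and the arms are near 30 each. The documents do not show that 5 cm causes more bleeding than 3 cm, and nothing here implies it. This is an inexpensive improvement worth making, not a flaw that undermines the pilot's endpoints.

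**What to change.** 1. Add a yes/no bleeding item to the existing post-swab CASI, unless one is already there, and tabulate it descriptively by depth in H.3.1.
2. Reconcile I.3, G.2 and Section L on which AEs are recorded and for how long, and correct the section pointer in the G.2 footnote.
3. State in H.3.1 which grades and which relatedness categories the AE table covers, so that an absence of low-grade events is not read as a finding.

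Expedited reporting is unchanged. The cost is one survey item, a few sentences and a few low-grade events logged. Two limits remain. A CASI completed immediately after swabbing would miss later bleeding, so its table should be labelled as bleeding noticed at the visit. With about 30 per arm, the by-depth figures can only be descriptive.
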